Likely contributors to above measures: Lipid/glucose markers:(fasting C-peptide and lipid panel, HbA1c); hepatic markers:(c-reactive protein, glucagon, GLP-1 and leptin at baseline, 5 min and 30 min post glucose load to asses change with OG, adiponectin, AST, ALT, GGT), sex-steroids:(DHEAS, free and total testosterone, sex hormone binding globulin, progesterone, estradiol); Body size and composition: (BMI, waist/hip ratio, DEXA, hepatic visceral fat via MRI³⁶⁻³⁹), Whole body fat oxidation at rest and following glucose ingestion as measured with a metabolic cart; Physical activity/ diet:(accelerometer, activity survey (3DPAR); Food frequency survey).Questionnaires for presence of obstructive sleep apnea. Questionnaires for perceived mental strengths and difficulty (note there is no assessment of suicidality on this tool). Obstructive Sleep Apnea, to be assessed with an overnight sleep study via WatchPAT.

B. Description of Population to be Enrolled:

Study staff aims to enroll 20 obese girls with regular menstrual cycles, 20 girls with un-treated PCOS, 20 girls with PCOS treated with at least 6 months of Metformin and 20 girls with PCOS treated with at least 6 months of oral contraceptives. The PCOS groups will be compared to 20 obese non-PCOS controls. This is the number of participants needed to be completed statistically, thus more subjects may be enrolled, to allow for screen failures and dropouts. Total enrollment will be up to 100 participants.

Ethnic Categories	Gender		
	Females	Males	Total
Hispanic or Latino	40	0	40
Not Hispanic or Latino	60	0	60
Ethnic Categories: Total of All Subjects	100	0	100
Racial Categories			
American Indian/Alaska Native	5	0	5
Asian	10	0	10

Native Hawaiian or Other Pacific Islander	10	0	10
Black or African American	32	0	32
White	43	0	43
Racial Categories: Total of All Subjects*	100	0	100

Inclusion Criteria:

- 1) Female
- 2) Ages 12-21
- 3) Sedentary- less than 2.5 hours of moderate (jogging, swimming etc) exercise a week.
- 4) BMI equal or greater than the 90th percentile for age and gender
- 5) For PCOS groups: (NIH definition) irregular menstrual cycles at least 1.5 years after menarche and either clinical evidence of hyperandrogenism or elevated Testosterone (above the norms for age/tanner stage) at time of screening or documented prior to initiation of therapy for OCP and metformin groups.

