- 6) For PCOS groups: patients un-treated or currently treated with either Metformin 1500-2000 mg a day or oral contraception (30-35 mcg ethynodiol a day) for at least 6 months, with > 80% adherence confirmed via refill frequency from pharmacy.
- 7) For non-PCOS groups: regular menstrual cycles at least 1.5 years after menarche and no clinical evidence of hyperandrogenism

Exclusion Criteria:

1. Use of medications known to affect insulin sensitivity: oral glucocorticoids within 10 days, atypical antipsychotics, immunosuppressant agents, HIV medications. Nexplanon, Depo-Provera or Mirena progesterone only contraceptives. Dermal patch or vaginal ring contraception methods. For controls only: metformin or oral contraception.
2. Currently pregnant or breastfeeding women. Development of pregnancy during the study period will necessitate withdrawal from the study.
3. Severe illness requiring hospitalization within 60 days
4. Diabetes, defined as Hemoglobin A1C > 6.4%
5. BMI percentile less than the 90th percentile for age and sex. Weight >325 lbs or <84 lbs.
6. Anemia, defined as Hemoglobin < 10 mg/dL
7. Diagnosed major psychiatric or developmental disorder limiting informed consent
8. Implanted metal devices that are not compatible with MRI
9. Use of blood pressure medications
10. Known liver disease other than NAFLD or AST or ALT >150 mg/mL

Rationale for Inclusion of Non-PCOS Subjects

Obese adolescents are at risk of T2D and its complications, reduced exercise capacity, increased liver and visceral fat, muscle dysfunction and cardiovascular dysfunction therefore the tests

performed screening for each of these problems provide useful information to these subjects. Likewise, sedentary subjects of any weight are at increased risk of reduced bone mineral density (BMD), T2D, reduced exercise capacity, increased liver and visceral fat, muscle dysfunction and cardiovascular dysfunction. Therefore, all of the subjects may benefit from the results of DEXA, glucose testing and exercise prescription and dietary counseling.

C. Study Design and Research Methods

Study Calendar	Visit 1 – Screen	Visit 2 –MRI	Visit 3 – Overnight
Consenting and Eligibility Assessment	X		
History & Physical	X		
Intravenous Blood Draw	X		X
Finger Stick Blood Draw		X	
Urine Pregnancy Test			X
Accelerometer Teaching	X		
Gut Bacteria Collection			X
Questionnaires- SEARCH Food frequency, Activity 3DPAR, Strengths and Difficulties and Sleep assessments			X

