DEXA Scan (located in Leprino building)			X
Oral Glycerol Tracer			X
WatchPAT sleep study			X
EndoPat and Dynapulse		X	
MRI of abdomen and liver,		X	
P MRS of Liver (pending scheduling)		X	
Metabolic Cart			X
Total Time of visit (approximately)	2 Hours	2 Hours	24 Hours
Location of Visit	CHCO CTRC Outpatient	UCD Outpatient Brain Imaging Center	CHCO Inpatient Hospital

The study consists of 3 visits - 2 outpatient visits and one overnight inpatient visit. Inpatient visit will last approximately 24 hours, outpatient screening visit approximately 2 hours, outpatient MRI visit approximately 2 hours. The 3 visits would be completed within 4 months' time.

Overall enrollment procedure plan per group

Test Group	Screening	MRI/MRS	Overnight stay	Oral Glycerol tracer	DEXA
Untreated PCOS	25	20	20	20	20
PCOS w/ Metformin	25	20	20	20	20
PCOS w/ OCP's	25	20	20	20	20
Obese Control	25	20	20	20	20
Total	100	80	80	80	80

VISIT 1 (SCREEN VISIT)

Pediatric CTRC Outpatient unit: Participants will begin with a medical screening and physical exam for inclusion/exclusion criteria evaluation. During this visit, patients will review and complete consent documents, have demographics and medical history confirmed, assess allergies and further evaluation of inclusion/exclusion criteria, have blood samples drawn, and have anthropometrics completed. HbA1c, ALT, AST, CBC panel and testosterone panel will be drawn at the beginning of the visit after consent in all subjects. PCOS subjects will have more labs performed for confirmation of PCOS status, if not performed previously.

Screening lab test	Purpose for test
HbA1C	Rule out type 2 diabetes, if > 6.4% subject to be excluded
ALT, AST	Ensure no severe liver disease, if >150 IU subject to be excluded normal subject is excluded
Hemoglobin & Hematocrit (part of CBC)	If subject is Anemic, they will be excluded
Testosterone	Test for hyperandrogenism – required to meet NIH criteria for PCOS
Optional PCOS labs	
PCOS status must be confirmed prior to enrollment in PCOS group. Referring physicians often do not perform the entire recommend work-up for oligomenorrhea (per 2013 Endocrine Society Clinical Guidelines for PCOS). The values are typically expected in PCOS publications	
TSH, total T4	Ensure no hypo or hyperthyroidism causing amenorrhea
LH, FSH	Rule out primary ovarian failure
17-hydroxyprogesterone	Rule out late onset congenital adrenal hyperplasia
DHEAS	Rule out adrenal tumor
Prolactin	Rule out prolactin secreting brain tumor

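### The diabetes exclusion rests on one screening HbA1c, which is an on-treatment value in the metformin group, so the metformin and untreated PCOS groups are screened differently

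*Combined protocol and SAP*

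**What the plan says.** Exclusion 4 (Section III.B) defines the condition by a laboratory cut-off: "Diabetes, defined as Hemoglobin A1C > 6.4" (per cent). The Visit 1 screening laboratory table gives the purpose and the action: "Rule out type 2 diabetes, if > 6.4% subject to be excluded". The timing is the same for everyone: "HbA1c, ALT, AST, CBC panel and testosterone panel will be drawn at the beginning of the visit after consent in all subjects". The Subject Discontinuation Criteria (Section VI.C, item 2) repeat the threshold as a screening-laboratory rule.

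Inclusion 6 takes untreated PCOS girls and also those "currently treated with either Metformin 1500-2000 mg a day or oral contraception (30-35 mcg ethynodiol a day) for at least 6 months". Pharmacy refills must show that treated girls took more than 80% of their drug. The medication exclusion bars metformin only in the comparison group without PCOS: "For controls only: metformin or oral contraception".

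For PCOS status the protocol does look back before treatment. Inclusion 5 accepts hyperandrogenism found "at time of screening or documented prior to initiation of therapy for OCP and metformin groups". Exclusion 4 has no such look-back.

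The Data Analysis Plan (Section VII, Secondary Aims, b) compares the untreated group with each treatment group separately.

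**The concern.** The same cut-off is applied to two different quantities. In the untreated PCOS group the screening HbA1c is untreated glycaemia. In the metformin group it is glycaemia after at least six months of a drug that the protocol itself expects to improve post-prandial glucose. A girl who would have failed the cut-off before therapy can pass it on therapy.

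Treatment is not randomised, so comparability of the groups rests on the entry criteria and the named adjustments. Section VII names ethnicity (if the groups differ on it) and sleep apnoea. For the non-isotope OGTT measures, groups are also compared with and without control for activity and sleep. None of these captures glycaemia before treatment. If the entry rule differs by group, nothing later in the plan corrects for it. The stated restriction to girls without type 2 diabetes is also not secured in the metformin group.

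**Working it through.** This is mainly a reading of the eligibility text, so the provisions are set side by side first.

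**1. What can exclude a girl for diabetes?**
- Exclusion 4: HbA1c above 6.4%.
- Visit 1 laboratory table: the same cut-off, one draw, all subjects.
- Section VI.C, item 2: the same cut-off again.
- Exclusion 1 (medication): metformin bars controls only, so metformin prescribed for diabetes does not bar a girl from the metformin group.
- Visit 1 history: medical history is confirmed, but no listed criterion makes a past diabetes diagnosis exclusionary. Exclusions 7 and 10 do refer to a diagnosed disorder and to known liver disease; Exclusion 4 has no comparable wording.

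**2. Two girls with the same HbA1c above 6.4% before any therapy.**
- Untreated at screening: her value is still above 6.4%, and she is excluded.
- On metformin for six months or more, with HbA1c now 6.4% or below: she passes Exclusion 4, meets Inclusion 6 if adherent, and is eligible.

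The asymmetry is limited to this case. A girl with a known diagnosis whose HbA1c is 6.4% or below without drug passes the written definition in any group. That is a gap in the definition, but not a difference between groups.

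**3. The plan's figure for the affected comparison.** Section VII states a power of 0.87 for 30 untreated versus 15 treated girls, difference 2, SD 2, alpha 0.05 (sidedness not stated; two-sided assumed).
- Standard error = 2 × √(1/30 + 1/15) = 0.632, and 2 / 0.632 = 3.16.
- Power by the noncentral t is 0.871; by the normal approximation, Φ(3.16 − 1.96) = 0.885.

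The stated figure reproduces, so the point concerns who enters the comparison and not the power calculation.

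**4. What would determine the size.** Let f be the share of such girls in the metformin group and s their mean flux shift against the expected metformin effect. The expected difference becomes 2 − f × s. The documents give neither f nor s, nor the sign of s. As an assumed range only:
- f = 0: difference 2, power unchanged.
- f = 10%, s = +2: 2 − 0.10 × 2 = 1.80, power about 0.79 (normal approximation, allowing for the added variance in the metformin group).
- f = 10%, s = −2: 2 + 0.10 × 2 = 2.20, so the apparent effect is enlarged.

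These lines show that the effect can be nil or go either way; they do not estimate it.

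**The case against.** The strongest reply is that the intent is plain. The excluded condition is named as diabetes, the test is there to rule out type 2 diabetes, and a history and physical are part of screening, so an investigator would be unlikely to enrol a girl known to have it. That is probably true of many cases. However, the written definition is closed, and a history can exclude only against a listed criterion.

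Second, one recruitment route narrows the gap. The Subject Recruitment Plan allows re-contact of girls from earlier PCOS protocols who were later prescribed metformin or an oral contraceptive, and Section VIII says previous protocols excluded type 2 diabetes. Girls from that route were screened before that prescription. This stands, but it covers only part of the group: recruitment also draws on endocrine, PCOS, Lifestyle, adolescent and gynaecology clinics and on the community.

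Third, non-randomised choice of treatment is the larger problem, and one eligibility sentence does not remove it. That also stands. Girls just under the cut-off before metformin would remain.

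In the other direction, a reader might infer that such girls would mask a metformin benefit, and might size this by giving each the plan's steatosis difference of 3, or the type 2 diabetes triglyceride mean in Table 1 (207 versus 129 mg/dL in PCOS). The documents do not support either step. The 3 is a steatosis contrast from a reference study in men, and the preliminary data report steatosis rates higher in PCOS than in type 2 diabetes girls. No flux value for diabetes is given. The Table 1 diabetes group has a mean HbA1c of 7.2%, whereas the girls at issue are at 6.4% or below by construction. Triglyceride concentration is listed as a likely contributor, not as a primary or secondary outcome.

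**Conclusion.** The point holds as a defect in an eligibility rule. As written, Exclusion 4 screens the metformin group on treated glycaemia and the untreated PCOS group on untreated glycaemia, and no other criterion closes the gap. It bears on one secondary comparison, metformin versus untreated, and on the stated aim of ruling out type 2 diabetes.

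The conclusion rests on two premises: that the criterion is applied as written, and that metformin can bring some girls from above 6.4% to 6.4% or below. It does not show that any such girl is or will be enrolled. The number, and the size and direction of any bias on the primary flux outcome, cannot be derived from the documents and may be zero. Severity: minor.

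**What to change.** Extend Exclusion 4 to cover (i) a prior diagnosis of diabetes, in all groups, and (ii) for the metformin and oral contraceptive groups, any documented HbA1c above 6.4% before therapy began. Keep the screening HbA1c rule for everyone. Item (ii) is the same kind of look-back that Inclusion 5 already uses for hyperandrogenism ("documented prior to initiation of therapy for OCP and metformin groups"). Align the Visit 1 laboratory table and Section VI.C, item 2 with the new wording.

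Record for each treated girl the pre-therapy HbA1c, or that none is available, and for each girl on metformin the indication for which it was prescribed. If any girl already enrolled meets the added criterion, repeat the metformin versus untreated comparison without her and report both results.

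The cost is one sentence in the criteria, two matching edits and two data items. A few treated girls may become ineligible. Girls with no pre-therapy HbA1c on record can be screened only on history and the current value; this is a real limit, since the protocol notes that referring physicians often leave the recommended oligomenorrhoea work-up incomplete.

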Minimizing Risk: Certain studies at our institution draw over 7ml/kg in 6 weeks, or up to 7 ml/kg in a single draw, but include iron supplementation. Otherwise, the routine guidelines in our Pediatric CTSC are 2.5ml/kg for a single draw and no more than 5 ml/kg over a 4 week period. Our baseline visit will include 11.5 ml of blood (HbA1c, Hb, Cr, AST, ALT) and 25.5 ml of blood for PCOS patients (additional draw for T4, TSH, prolactin, LH, FSH, 17OH progesterone and DHEAS). The OGTT visit includes up to 300 ml of blood which will occur within 4 weeks of the initial visit. Thus, our OGTT visit is within the NIH Clinical Center guidelines of 9 ml/kg in 6-8 weeks and within Children's Hospital Colorado's institutional guidelines of 5 ml/kg. In addition, by study design, subjects are screened by our baseline CBC and excluded if anemic, further increasing the safety of the study regarding blood draws. We will use a minimum weight cutoff of 38 kg to remain below the most conservative pediatric CTSC blood drawing guidelines. This screening also helps to increase the safety of the blood draw. In addition, the blood planned to be frozen and held could also be

omitted if needed to reduce blood volume for a particular subject. Finally, our CTRC has a system to track other studies subjects might enroll in, and we ask during our consent process if the subject has been involved in any other studies in the past 6 weeks to avoid excessive blood drawing.

Justification: Screening laboratory measurements are necessary to assure that patients meet inclusion/exclusion criteria before any further study is completed. A CBC is necessary as a screening lab, to rule out anemia. A hemoglobin A1c can be used to rule out diabetes. Hormone levels of free and total testosterone, and sex hormone binding globulin are needed to categorize patients as having PCOS, and prolactin, DHEAS, LH, FSH, TSH, total T4 or 17-OH progesterone to rule out other causes of oligomenorrhea, if not done previously.

2. IV Risks

Description: One peripheral IV will be placed during the OGTT for drawing blood samples.

Risk: There is temporary discomfort when the needle goes in and 10% of the time there is a small amount of bleeding under the skin that may produce a bruise. Rarely, there is a risk of a blood clot forming or infection. We will use a low dose of a medication called heparin to try to prevent blood clotting.

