1. Serious Adverse Event Definition

Events are divided into those that are not serious (AE) and those that are serious (SAE). The distinction between an SAE and an AE is a regulatory definition established by the FDA, not a clinical definition. The definition of SAE is not always related to clinical severity of the event. For the purposes of this study an AE is considered a Serious (SAE) when it satisfies any one of the following criteria:

- The event results in an inpatient hospitalization (any overnight stay associated with an admission).
- The event results in the prolongation of a hospital stay.
- The event results in permanent or severe disability.
- The event results in death.
- The event is life-threatening.
- Treatment is required to prevent a serious event.

There have been no SAE's in the research groups experience in the Pediatric CTRC. We do not anticipate encountering SAE's; however, we have identified the following as possible SAE's for the purposes of monitoring:

- Infection related to blood draw or IV placement

a) Serious Adverse Event Reporting

Study patients are instructed to contact the clinic with any serious adverse event meeting the above criteria. Each SAE is recorded on the study form and the PI is informed as soon as possible after they occur and preferably within 24 hours of the notification of the clinic staff. This notification should occur even if data are incomplete. Additional data and follow-up information are documented and sent subsequently as an update to the original report. The PI immediately forwards SAE reports to the COMIRB and any other required institutional monitoring committee.

C. Subject Discontinuation Criteria

If a subject experiences any of the following, the subject will be withdrawn from the study.

1. Inability to complete study procedures
2. Abnormal screening labs (LFT's >150 IU, HbA1C>6.4%, Hg <10 mg/dL)
3. Subject becomes pregnant during study

D. Protocol Stopping Criteria

If one or more subjects experience any of the SAE's listed above, the PI will consult with the study staff prior to continuing study visits with subjects. The PI and RSA will consult about the significance of the SAE's and make a recommendation about subject continuation in the study.

VII. Data Analysis Plan:

Overall Project Statistical Plan:

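### The haemoglobin limit for exclusion and withdrawal is written in mg/dL (a thousandfold too low if g/dL is meant), and exclusion criterion 10 gives the AST/ALT limit in a mass unit

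*Combined protocol and SAP*

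**What the plan says.** **Haemoglobin.** A numeric limit appears in two places.

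- Section III.B, Exclusion Criteria, item 6: "Anemia, defined as Hemoglobin < 10 mg/dL".
- Section VI.C, Subject Discontinuation Criteria, item 2: "Abnormal screening labs (LFT's >150 IU, HbA1C>6.4%, Hg <10 mg/dL".

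Three further statements rely on the limit without giving a number.

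- The Visit 1 screening lab table (section III.C): "If subject is Anemic, they will be excluded".
- Section III.D.1, Blood Sampling, on the purpose of the test: "A CBC is necessary as a screening lab, to rule out anemia".
- The same section, on minimising risk: "subjects are screened by our baseline CBC and excluded if anemic, further increasing the safety of the study regarding blood draws". The draw in question is also described there: "The OGTT visit includes up to 300 ml of blood".

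**AST/ALT.** The limit appears in three places.

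- Section III.B, Exclusion Criteria, item 10: "Known liver disease other than NAFLD or AST or ALT >150 mg/mL".
- The Visit 1 screening lab table: "Ensure no severe liver disease, if >150 IU subject to be excluded".
- Section VI.C, item 2, quoted above, which also uses IU.

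Table 1 in the preliminary studies reports AST and ALT in IU/L.

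**The concern.** Both limits decide who may enter or stay in the study, and both carry the wrong unit.

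The haemoglobin error is the more important of the two because nothing in the document corrects it. Both numeric statements use the same wrong unit, and the other statements only say that anaemic girls are excluded. Taken at its word, the criterion cannot be met by anyone, so it does not do what the screening table and the Blood Sampling section say it does. A girl with a haemoglobin of 9 g/dL shows the conflict: withdrawing her contradicts the written number, and keeping her contradicts those two sections.

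The protocol presents the anaemia screen as a protection around a sizeable blood draw. It is one of several: there is also a minimum weight of 38 kg, the option to omit stored blood, and tracking of other studies. It still matters most for the lightest eligible participants.

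For AST/ALT the stake is consistency. One threshold is expressed in two kinds of unit, and the formal exclusion list holds the one that cannot be compared with a laboratory's enzyme-activity result.

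**Working it through.** No sample size, power or alpha figure is involved. The check is unit conversion and a comparison of the statements.

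**1. Haemoglobin, as written.** Input: 10 mg/dL (III.B item 6; VI.C item 2, reading Hg as haemoglobin).

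- 10 mg/dL ÷ 1,000 mg per g = 0.01 g/dL.
- Assumed intended limit: 10 g/dL = 10 × 1,000 = 10,000 mg/dL.
- Ratio of written to assumed intended: 10 / 10,000 = 1/1,000.

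The documents never state g/dL. That unit is inferred from physiology, and from the fact that the number 10 gives a limit able to identify anaemia only on the g/dL scale.

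**2. AST/ALT, as written in criterion 10.** Input: 150 mg/mL.

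- 150 mg/mL = 150 g/L = 15 g/dL.

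This is a mass of substance per volume. It cannot be compared with a result reported as enzyme activity.

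**3. Which scale does 150 belong to?** Table 1 group means, in IU/L:

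| | Control | PCOS | T2D |
|---|---|---|---|
| AST | 19 | 36 | 32 |
| 150 / AST | 7.9 | 4.2 | 4.7 |
| ALT | 29 | 38 | 40 |
| 150 / ALT | 5.2 | 3.9 | 3.75 |

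The limit is 3.75 to 7.9 times the group means. Diabetes is an exclusion here, so the control and PCOS columns are the relevant ones, and they give 3.9 to 7.9. Either way, 150 IU/L is a plausible cut-off for marked elevation.

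**4. Count of statements.**

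| Limit | Places with a number | Unit as written |
|---|---|---|
| Haemoglobin | III.B item 6; VI.C item 2 | mg/dL in both |
| AST/ALT | III.B item 10 | mg/mL |
| AST/ALT | Visit 1 screening table; VI.C item 2 | IU, no volume |

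Haemoglobin is wrong in 2 of 2 places. AST/ALT has the wrong kind of unit in 1 of 3 and an incomplete unit in the other 2.

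**5. Context for the blood draw.** At the 38 kg minimum in III.D.1, the maximum draw is 300 / 38 = 7.9 ml/kg. The weight at which 300 ml equals the 5 ml/kg institutional guideline cited there is 300 / 5 = 60 kg. Since 300 ml is a ceiling and stored samples can be dropped, this does not show that harm is expected. It shows that the anaemia screen has a real role for lighter participants.

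**The case against.** The best answer is that nobody would apply the literal reading. Criterion 6 opens by naming anaemia, the screening table and Blood Sampling section repeat that anaemic girls are excluded, and no competing number exists. A clinician would read 10 as g/dL, so a girl known to be anaemic would not be enrolled. On this view it is a clerical slip with no analytic consequence. That largely stands as a statement about likely practice, and it is why the effect is judged small. It does not make the written threshold right: eligibility and withdrawal are audited against the text of the criterion, and the text gives no correct value anywhere.

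Three narrower points also carry some weight.

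- The discontinuation item restates the Visit 1 screening result, and the plan describes no later haemoglobin check. The two haemoglobin statements are therefore one check written twice. Both still need the same correction.
- The AST/ALT slip is covered in practice by the 150 IU in the screening table and in section VI.C. This is true, and on its own it would be a minor inconsistency.
- Completing IU to IU/L is close to house style, since Table 1 already shows the unit. This is fair. It is included only because those lines are being edited anyway.

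**Conclusion.** The concern holds. The haemoglobin limit is wrong as written in both places where a number is given, at 1/1,000 of 10 g/dL, and nothing else in the document corrects it. The AST/ALT limit in criterion 10 is in a mass unit and conflicts with the other two statements of the same limit and with Table 1.

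The expected practical effect is small: staff would probably apply 10 g/dL, and a working AST/ALT limit of 150 IU exists elsewhere. Power, endpoints and analysis are not affected. The correction is still worth making because these are operative safety thresholds and not background text.

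The conclusion that the haemoglobin limit cannot be triggered as written rests on the conversion and basic physiology. The replacement value rests on one assumption, that g/dL was intended, which the sponsor should confirm. For AST/ALT, the protocol's own IU statements and Table 1 support IU/L.

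**What to change.** 1. In section III.B item 6 and section VI.C item 2, change the haemoglobin limit to < 10 g/dL, once the sponsor confirms that value.
2. In section III.B item 10, change the AST/ALT limit to > 150 IU/L.
3. In the same edit, complete IU to IU/L in the Visit 1 screening lab table and in section VI.C item 2, so that all three statements match each other and Table 1.

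The cost is three unit corrections and two unit completions. No visits, procedures or data collection are added.

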Accelerometer: One week prior to visit 3, the subject will be provided two accelerometers (GT3X BT by Actigraph and ActiWatch by Philips Respironics) to be worn for seven days to measure level of habitual physical activity, which affects insulin sensitivity, and sleep patterns. Accelerometers are effective tools for the objective measurement of physical activity ⁴⁴ because they have the ability to continuously record physical activity data and such data can be used to estimate METs of activity. They provide more detailed information than pedometers, which only measure walking steps, and help get around the recall bias of questionnaires. We are currently using the GT3X BT Actigraph in adolescents in our other diabetes studies; therefore, we are familiar with their use in this population and have the necessary computer software and interpretation skills. The Actiwatch is being used as a tool for objective measurement of sleep patterns. The Actiwatch is fitted with a LED monitor that detects multiple spectrums of light to better assess sleep patterns in this population.

One week prior to visit 3, participant will receive via mail the accelerometer, sleep diary and stool sample collection kit (Gut bacteria collection)

VISIT 3 (ORAL GLUCOSE TOLERANCE TEST WITH ORAL GLYCEROL TRACER)

Pediatric CTRC Inpatient unit: Subjects will be asked not to have caffeine or exercise for 3 days prior to this visit. During admission, subjects will be provided with a study diet dinner and snack. Patients will be admitted to the Pediatric CTRC for a monitored overnight fast. Subjects will be questioned regarding changes in concomitant medications and medical history, height, weight, BP.

A DEXA scan will be performed to assess body composition. A urine pregnancy test will be done on all female subjects prior to the DEXA scan. If a female subject is confirmed to be pregnant, she will be withdrawn from the study and referred to her primary care physician for follow-up.

The following morning, a blood sample for baseline metabolic labs will be drawn the modified OGTT will be completed. DNA extract-and-hold samples for future genetic analysis associated with hepatic steatosis will also be drawn and stored at this time. Additional blood will be drawn and stored for future inflammatory markers as well as for targeted and untargeted metabolomics analysis.

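### The 38 kg weight floor does not keep a 300 ml OGTT visit within the 5 ml/kg blood limit the protocol claims; at full volume the limit is met only from 60 kg

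*Combined protocol and SAP*

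**What the plan says.** Section III.D.1 (Blood Sampling, Minimizing Risk) gives the routine pediatric research-unit limits as 2.5 ml/kg for one draw and "no more than 5 ml/kg over a 4 week period". On the planned volume it says: "The OGTT visit includes up to 300 ml of blood which will occur within 4 weeks of the initial visit". It then concludes, without condition, that the visit meets the NIH guideline of 9 ml/kg in 6-8 weeks and is also "within Children's Hospital Colorado's institutional guidelines of 5 ml/kg". The weight floor is justified in these words: "We will use a minimum weight cutoff of 38 kg to remain below the most conservative pediatric CTSC blood drawing guidelines".

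Exclusion criterion 5 in Section III.B puts the same floor into effect: "Weight >325 lbs or <84 lbs".

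Screening takes a further 11.5 ml, or 25.5 ml in PCOS patients who need the additional work-up. Section III.C, Visit 1, makes that extra blood conditional: "PCOS subjects will have more labs performed for confirmation of PCOS status, if not performed previously".

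The one provision for reducing volume, also in III.D.1, is that blood meant to be frozen and held could be "omitted if needed to reduce blood volume for a particular subject".

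**The concern.** Three figures in one paragraph have to agree: a 300 ml ceiling, a 5 ml/kg limit and a 38 kg floor. They do not, because 5 ml/kg at 38 kg is well short of 300 ml.

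This is a participant-safety matter. No endpoint, power figure or analysis depends on it. But eligibility starts at age 12, and the floor is one of the safeguards the IRB is asked to rely on against excessive blood loss. Staff who trust the stated floor would see no reason to reduce the volume in a girl of 45 or 55 kg, although the full visit would take her over the limit the protocol says it respects.

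**Working it through.** **Inputs.** From Section III.D.1: OGTT visit up to 300 ml; limits of 5 ml/kg over four weeks and 9 ml/kg over 6-8 weeks; floor 38 kg; screening 11.5 ml, or 25.5 ml with the PCOS work-up. From Section III.B: floor 84 lb, and 84 × 0.4536 = 38.1 kg, so the two statements of the floor agree and 38 kg is not a misprint.

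**Can the 38 kg floor be reproduced?** The lowest weight that satisfies a limit is volume ÷ limit.

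| Blood counted | Volume (ml) | Lowest weight at 5 ml/kg | Lowest weight at 9 ml/kg |
|---|---|---|---|
| OGTT visit only | 300 | 60.0 kg | 33.3 kg |
| plus 11.5 ml screening | 311.5 | 62.3 kg | 34.6 kg |
| plus 25.5 ml screening | 325.5 | 65.1 kg | 36.2 kg |

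The floor of 38 kg satisfies the 9 ml/kg limit in every row and the 5 ml/kg limit in none.

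**Dose of blood loss by weight.** The draw per kg is 300 ÷ weight, the allowance is 5 × weight, and the room left for the OGTT after a 25.5 ml screening draw is 5 × weight − 25.5.

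| Weight (kg) | 300 ml as ml/kg | Allowance at 5 ml/kg (ml) | Excess, OGTT alone (ml) | OGTT volume that fits after 25.5 ml (ml) | Cut from 300 ml |
|---|---|---|---|---|---|
| 38 | 7.9 | 190 | 110 | 164.5 | 135.5 ml (45%) |
| 45 | 6.7 | 225 | 75 | 199.5 | 100.5 ml (34%) |
| 50 | 6.0 | 250 | 50 | 224.5 | 75.5 ml (25%) |
| 55 | 5.5 | 275 | 25 | 249.5 | 50.5 ml (17%) |
| 60 | 5.0 | 300 | 0 | 274.5 | 25.5 ml (8.5%) |

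With the smaller screening draw, the volume that fits at 38 kg is 190 − 11.5 = 178.5 ml, a cut of 121.5 ml (40.5%).

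**Cumulative draw at 38 kg.** 311.5 ÷ 38 = 8.2 ml/kg and 325.5 ÷ 38 = 8.6 ml/kg. Both stay under 9 ml/kg (9 × 38 = 342 ml), so the NIH statement is correct. The 8.6 figure is an upper case, for a PCOS patient whose full work-up had not been done before.

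**Left out.** Whether the 2.5 ml/kg single-draw limit covers serial sampling over 6.5 hours is a matter of interpretation, and nothing here rests on it.

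**The case against.** The case on the other side has five parts.

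- **300 ml is a ceiling, and held blood may be omitted.** Drawing the full amount from a 38 kg girl would ignore the protocol's stated aim and leave its reduction unused. This is fair as to what careful staff would do. But compliance is claimed for the visit defined by that ceiling, and no other OGTT volume is given. The omission is optional, has no weight trigger and has no stated volume. At 38 kg it would have to supply 110 to 135.5 ml, and nothing shows that so much is held.
- **Very few girls will be near 38 kg.** Section III.B requires BMI at or above the 90th percentile and menstrual history at least 1.5 years after menarche. The protocol gives no BMI cut-points. If the 90th percentile is assumed to be 22-26 kg/m², the greatest height compatible with a given weight is √(weight ÷ BMI): 1.21-1.31 m at 38 kg, 1.39-1.51 m at 50 kg and 1.52-1.65 m at 60 kg. On that assumption the realistic exposure is roughly 50-60 kg, or 5 to 6 ml/kg at full volume. This stands, and it makes the likely excess smaller than the figure at the floor. It does not remove the excess, since girls below 60 kg remain eligible.
- **The NIH limit holds at the floor.** True, but the protocol claims both limits.
- **There are other safeguards.** Anemia is excluded, and participation in other studies is tracked and asked about. These lower the risk from a draw without making the 5 ml/kg statement correct.
- **Screening blood may not count.** Section III.C lets the three visits span four months, although III.D.1 says the OGTT follows within four weeks. With a longer gap, the 62.3 and 65.1 kg thresholds fall away. The 60 kg threshold for the OGTT visit alone does not.

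**Conclusion.** The concern holds. The statement that a visit of up to 300 ml is within 5 ml/kg is wrong for any participant under 60 kg drawn at the ceiling, and the 38 kg floor does not deliver the limit it is offered to protect. The largest excess for the OGTT visit alone is 110 ml (7.9 against 5 ml/kg, at 38 kg), falling to zero at 60 kg. With screening blood in the same four weeks, the threshold rises to 62.3-65.1 kg.

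These figures rest on the full 300 ml being drawn; the cumulative ones also rest on the four-week interval. The number of girls affected is unknown and may be small. The point should still be corrected, because it is a wrong safety threshold in a study that enrols minors.

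**What to change.** Replace the optional omission in Section III.D.1 with a binding cap: blood from screening plus the OGTT visit within any four weeks must not exceed 5 ml/kg. At 38 kg that is 190 ml in total, or 164.5 ml at the OGTT after a 25.5 ml screening draw. For girls below about 60-65 kg, drop the freeze-and-hold blood first, and state its volume so that the cap can be checked.

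If the cap cannot be met without losing endpoint samples, there are two alternatives. One is to raise the floor in criterion 5 and Section III.D.1 together. The other is to remove the 5 ml/kg and most-conservative claims and tell the IRB that only the NIH limit is met at the floor.

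The cost is a short amendment and less stored blood in lighter girls. Some of that may be metabolomics material, which serves Aim 2, since Section III.C, Visit 3, says: "Additional blood will be drawn and stored for future inflammatory markers as well as for targeted and untargeted metabolomics analysis". Raising the floor would instead make some lighter girls ineligible. Neither loss can be sized, because the protocol gives neither the held volume nor a weight distribution.
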